10.4.2 Safety

Acute safety outcome will be reported as the number of primary adverse events and the number and percentage of subjects experiencing primary adverse events (within 7 days of catheter ablation, with exception for PV stenosis and AE fistula).

The number and percentage of subjects with early onset (within 7 days of ablation procedure with exception for PV stenosis and AE fistula) pre-defined primary Adverse Events will be summarized overall and by AE type, severity, causality, anticipated or not and outcome etc. The primary adverse events will also be listed.

The number and percentage of subjects with Serious Adverse Device Effects (SADEs) during follow-up period (3 months) will be summarized overall and by AE type, timing (< 7 days, 7-30 days, > 30 days), seriousness, severity, causality, anticipated or not and outcome etc. Listing of SADEs will also be provided. The safety analysis will be performed in the safety populations.

10.4.3 Procedural Data

Procedural data will be summarized in the safety and effectiveness populations and listed in the safety populations. For continuous variables, the number of subjects with non-missing data, mean, standard deviation, median, 25% percentile, 75% percentile, minimum, and maximum will be reported. For categorical variables, the frequency and percentage will be presented for each category.

10.4.4 Investigational Device Performance

Investigational device performance will be reported by means of survey questions. The scores of survey questions will be summarized by presenting the number of subjects with non-missing data, mean, standard deviation, median, minimum, and maximum for each sub-scale measurement. Listings of survey answers/scoring will also be provided. The analysis will be performed in the effectiveness populations.

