8.4 Subject Disposition

The following subject groups are defined:

- **Enrolled subjects**: subjects who have signed and dated the Informed Consent Form
- **Excluded subjects**: subjects who are enrolled but never undergo the insertion of the investigational device. Excluded subjects will not be included in the safety or functionality evaluation of the investigational device.
- **Discontinued subjects**: subjects who are enrolled and have the investigational device inserted but no RF energy is administered by the investigational device. Discontinued subjects will remain in the safety cohort. These subjects will be followed-up until 7 days post-procedure for safety purpose.
- **Evaluable subjects**: subjects who are enrolled and meet the eligibility criteria and who undergo ablation with the study catheter.
- **Lost to Follow-up subjects**: subjects who are enrolled and evaluable, but contact is lost after most recent follow-up visit (despite 3 documented attempts to contact the subject).
- **Withdrawn / Early Termination Subjects**: subjects who withdraw consent for study participation or are withdrawn by the investigator (as described in Section 8.5) or are terminated from the study prior to completion of all follow-up visits.
- **Completed subjects**: subjects who are enrolled and that have not expired, been excluded, discontinued, withdrawn, terminated early or lost to follow-up from the study, prior to the final study visit.

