11.3.5 Investigational device performance

Investigational device performance (THERMOCOOL SMARTTOUCH® SF-5D Catheter (D-1395-05-SI) and nMARQ™ Multi-Channel RF Generator (D-1341-07) with Software V. 3.0.1, will be reported by means of survey questions. The scores of survey questions will be summarized by presenting the number of subjects with non-missing data, mean, standard deviation, median, minimum, and maximum for each sub-scale measurement. Listings of survey answers/scoring will also be provided. Workflow questions and interactions with system setup (Dongle (EM-5050-055F), Interface Cable (D-1357-03-SI), and CARTO 3 v6) might also be subjected to investigator feedback.

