5.2 Secondary Endpoints and associated hypotheses

- **Safety**

- Incidence of early onset (within 7 days of ablation procedure) primary Adverse Events.

Serious Adverse Events occurring within the first week (7 days) following an ablation procedure with the THERMOCOOL SMARTTOUCH® SF-5D catheter and AE term is one of the adverse events listed, will be considered for Primary Event assessment

Table 1 Primary Adverse Events

• Death
• Atria-Esophageal Fistula*
• Cardiac Tamponade/Perforation*
• Myocardial Infarction
• Stroke/Cerebrovascular Accident
• Thromboembolism
• Transient Ischemic Attack
• Diaphragmatic Paralysis
• Pneumothorax
• Heart Block
• Pulmonary Vein Stenosis*
• Pulmonary Edema (Respiratory Insufficiency)
• Vagal Nerve Injury
• Pericarditis
• Major Vascular Access Complication/Bleeding

* Pulmonary vein (PV) stenosis, atrio-esophageal fistula and cardiac tamponade/perforation that occurs greater than one week (7days) post-procedure shall be deemed Primary AEs.

- Incidence of Serious Adverse Device Effects (SADEs) during follow-up period (3 month)
- **Procedural data**
 - Rate for touch-up RF application post adenosine and/ or isoproterenol challenge
 - Target sites for RF lesion application
 - o Target sites
 - o Number of RF applications per target
 - o Total RF duration per application (sec)
 - Ablation parameters, including but not limited to:
 - o Total RF ablation time
 - o Temperature (generator files)
 - o Contact Force (CARTO® datafiles)
 - o Power (generator files)
 - o Impedance
 - Total Fluoroscopy time/dose
 - Total procedure time

- ECG data

- **Investigational device performance (rating with survey):**

- Contact and stability of catheter
- Signal Quality
- Temperature visualization
- Ease of use

6 Levels of Significance

All data will be summarized by descriptive statistics. No formal statistical inference will be performed.

7 Analysis Sets

The following analysis populations will be used to complete the analyses of data:

Safety Population 1: The Safety population 1 will include all subjects enrolled under protocol version 1.0 who have the investigational device inserted, regardless if RF energy is delivered.

Safety Population 2: The Safety population 2 will include all subjects enrolled under protocol version 2.0 who have the investigational device inserted, regardless if RF energy is delivered.

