Effectiveness Population 1: The effectiveness population will include all subjects enrolled under protocol version 1.0 who meet all eligibility criteria and have had the investigational device inserted and underwent ablation with the study catheter under guidance of the THERMOCOOL SMARTTOUCH® SF-5D Module.

Effectiveness Population 2: The effectiveness population will include all subjects enrolled under protocol version 2.0 who meet all eligibility criteria and have had the investigational device inserted and underwent ablation with the study catheter under guidance of the THERMOCOOL SMARTTOUCH® SF-5D Module.

8 Sample Size Justification

This is a clinical feasibility study for evaluation of workflow and acute performance of THERMOCOOL SMARTTOUCH® SF-5D system. This clinical investigation is intended to provide preliminary estimates of workflow and acute outcomes.

Because this study is a feasibility study, there is no statistical power calculation and no hypothesis to be generated. Fifty subjects are deemed sufficient to characterize the workflow and acute outcomes.

Enrollment in the clinical investigation will be approximately 50 evaluable subjects with approximately 10 subjects per investigational site, distributed over approximately 5 centers in Europe. The study catheter was redesigned in protocol v2.0. The total enrollment remains as approximately 50 evaluable subjects combining subjects enrolled under protocol v1.0 and v2.0.

9 Data Monitoring Committee (DMC)

The medical safety officer or designee will review, on regular or urgent basis, all applicable adverse events and deaths. This medical safety officer shall advise about the appropriateness of continuing or terminating the clinical investigation, based upon findings during his review of adverse events and deaths. The overall safety profile of the investigational device will be evaluated by the Sponsor at the end of the trial.

10 Analyses to be Conducted

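### The device-performance survey is summarized only in eligible, ablated subjects, so any ratings from inserted-but-no-RF procedures are left out, which can make the scores optimistic by an unknown amount

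*SAP*

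**What the plan says.** The survey is a secondary endpoint in both documents. It covers ease of use, signal quality, temperature visualization, and catheter contact and stability. Protocol 11.3.5 says that performance of the catheter and the RF generator "will be reported by means of survey questions" and names no analysis population. SAP 10.4.4 adds one: "The analysis will be performed in the effectiveness populations". The planned statistics are the number of non-missing scores, mean, SD, median, minimum and maximum, plus listings of the answers.

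SAP section 7 defines both effectiveness populations (one for each protocol version) as subjects "who meet all eligibility criteria and have had the investigational device inserted and underwent ablation with the study catheter under guidance" of the study module. The safety populations are wider: subjects "who have the investigational device inserted, regardless if RF energy is delivered".

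Protocol 8.4 names the group that lies between the two. Discontinued subjects are "subjects who are enrolled and have the investigational device inserted but no RF energy is administered by the investigational device", and "Discontinued subjects will remain in the safety cohort".

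For procedural data, SAP 10.4.3 uses both sets: "Procedural data will be summarized in the safety and effectiveness populations and listed in the safety populations".

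**The concern.** Several survey items could plausibly be rated once the catheter is in the heart, before any RF. A procedure given up at that stage because of poor signal, unstable contact or a set-up fault would be informative about usability. Under SAP 10.4.4 it does not count. Whether a rating is summarized can therefore depend on how the rated device behaved.

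The eligibility condition removes a second group. The effectiveness population in Protocol 11.2 has no such condition; the SAP adds it. An eligibility breach has no evident bearing on how a catheter handles.

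The study is purely descriptive, so the choice of analysis set fixes what is reported. SAP section 1 also records that the catheter was redesigned after a safety stop, which makes ratings from failed uses of the new design worth keeping.

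**Working it through.** The documents give no survey figure to reproduce: no scale, no expected scores and no expected number of discontinued subjects. The check is therefore a comparison of sets, followed by a formula with stated assumptions.

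**Step 1: who is in which set (SAP section 7, Protocol 8.4)**

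| Subject | Safety | Effectiveness | Procedural data (10.4.3) | Survey summary (10.4.4) |
|---|---|---|---|---|
| Eligible, ablated under module guidance | yes | yes | yes | yes |
| Inserted, no RF | yes | no | yes | **no** |
| Ablated, eligibility breach | yes | no | yes | **no** |
| Never inserted | no | no | no | no |

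Rows two and three are the loss. Protocol 8.4 bars only never-inserted subjects from the safety or functionality evaluation. That suggests insertion, not RF delivery, as its boundary for judging function.

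**Step 2: shift in the mean.** Let n be the subjects in the planned summary, d the omitted subjects with a completed survey, and g the mean score in the n minus the mean score in the d. Then

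planned mean − mean with the omitted subjects restored = d/(n + d) × g.

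Take n = 50 − 8 = 42. This comes from the SAP's total of about 50 evaluable subjects and its 8 subjects under protocol version 1.0, assuming that all 8 count as evaluable. The values of d and g are assumptions; g = 4 is the largest gap possible on an assumed 5-point scale.

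| d | d/(n + d) | g = −1 | g = 1 | g = 4 |
|---|---|---|---|---|
| 0 | 0 | 0 | 0 | 0 |
| 1 | 1/43 = 0.023 | −0.02 | 0.02 | 0.09 |
| 2 | 2/44 = 0.045 | −0.05 | 0.05 | 0.18 |
| 5 | 5/47 = 0.106 | −0.11 | 0.11 | 0.43 |

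The shift takes the sign of g, which is unknown. One worked illustration, wholly on assumed figures: of 42 insertions, 40 are ablated and average 4.5, and 2 deliver no RF and are rated 1. The planned mean is 4.50; the mean over all insertions is (40 × 4.5 + 2 × 1)/42 = 182/42 = 4.33. The mean moves little, but the reported minimum can change with a single omitted rating.

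**Step 3: chance that the issue arises.** The probability of at least one no-RF subject among N insertions at rate p is 1 − (1 − p)^N. The rates are assumed. With N = 50 it is 22% at p = 0.5%, 39% at 1%, 64% at 2% and 92% at 5%.

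**The case against.** A reader might infer that the survey scores are biased upward. The documents do not support that. It needs at least one no-RF case, a survey completed for that case, and a lower rating in it; none of these is established. The eligibility exclusion has no known direction at all.

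The strongest case for leaving the text alone runs as follows:

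- The ablated set is defensible. The study purpose concerns mapping and RF ablation procedures, and the survey covers the RF generator as well as the catheter. Generator performance and temperature visualization can hardly be rated without RF. The survey form is not in the documents, so it is an assumption that the other items can be rated without RF.
- The loss is narrow. A subject is discontinued only if no RF at all is given. Poor contact or signal after ablation has begun does not remove anyone, and some no-RF cases will have causes unrelated to the device. The 8 subjects under version 1.0 are described as treated; if that means ablated, the no-RF issue concerns version 2.0 only.
- Abandoned procedures show elsewhere: in disposition for all enrolled subjects (SAP 10.2), in procedural data for the safety populations (SAP 10.4.3), and in device-deficiency reporting (Protocol 10.7 and 10.8.3).
- Survey listings are planned, and their population is not separately named.

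These points reduce the issue and rule out a claim of demonstrated bias. They do not bring the ratings back. Disposition and deficiency records are not operator scores. The only population named in SAP 10.4.4 is the effectiveness populations, whereas SAP 10.4.3 says so explicitly when it wants safety-population listings. Items that need RF can be marked not applicable without discarding the rest of the form.

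**Conclusion.** The survey summaries leave out any ratings from inserted-but-no-RF procedures and from ablated subjects with an eligibility breach. This follows directly from the definitions. Because a device or set-up problem can be the reason no RF was given, the scores can be optimistic.

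The size and sign of the effect cannot be derived. It is zero if no such subjects occur, or if no survey is completed for them, since SAP 10.6 summarizes available data only. Otherwise it is about 0.02 per omitted rating per point of score gap at n = 42, in either direction. The 4.50 versus 4.33 comparison is illustrative only.

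Severity is low. The endpoint is secondary and descriptive, no inference is planned, and no primary or safety result changes. It is a cheap improvement worth making, not a flaw in the study's main conclusions.

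**What to change.** Replace the last sentence of SAP 10.4.4 with: *Survey scores will be summarized for both the safety and the effectiveness populations, and individual answers listed for the safety populations, as in 10.4.3; items that need RF delivery are scored not applicable when no RF was given.*

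Have the operator complete the survey for every procedure in which the investigational catheter was inserted. Neither document currently says whether a survey is done when no RF is delivered, and without one the change of population has no effect for those subjects.

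The planned effectiveness-population analysis is kept. The cost is one SAP sentence, one extra form for each no-RF insertion, and scores that may be slightly lower. The SAP approvals are dated August 2018, against a protocol version of November 2017, and the documents do not state enrolment status at that date. For procedures already done without a survey, the rating may not be recoverable; the number of such procedures should then be reported beside the scores.

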10.5 Plans for Interim Analysis

No interim analyses are planned for this study.

10.5.1 Stopping Rules

The clinical investigation team will review and monitor the clinical safety data on a regular basis for any safety or catheter design issues. Should the team identify any safety issues, the impacted clinical sites, EC's and CA's will be immediately notified to ensure the safety of their patients and the study may be stopped.

The sponsor may either suspend or prematurely terminate the study for significant and documented reasons.

A principal investigator, EC, or regulatory authority may suspend or prematurely terminate participation in the study at the study sites for which they are responsible.

10.6 Handling of Missing Data

Missing questions will be queried for reasons and handled on an individual basis. Summary statistics will be reported based upon available data only.

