9.2.3.1.8 Post-Ablation

- Verification of entrance block is required for all PVs.
 - **A 20-minute waiting period is REQUIRED from the last RF application at a PV before verification may be confirmed.** The time of the last RF application in a PV and the time of entrance block verification MUST be documented in the medical record as source documentation. If reconnection is noted, additional RF applications should be applied. A second and/or third waiting period will be upon investigator's discretion.
 - **Mapping the Ablation lines with the Study catheter's micro electrodes is REQUIRED during the 20-minute waiting period.** If

breaks in the RF lines are found additional RF applications should be applied.

- To verify entrance block, analyze electrograms in sinus and/or atrial paced rhythm to confirm that no PV potentials are present.
 - After a **REQUIRED** 20-minute waiting period, administer:
 - Adenosine (24mg bolus) to rule out dormant conduction and/or
 - Isoproterenol: to achieve a \geq 20 beats per minute increase in heart rate to induce AF upon completion of the ablation procedure (recommended dose range is 2-20 mcg/min).
- Demonstration of entrance block MUST be confirmed and documented by the Lasso® or Pentaray® Circular Mapping Catheter.
- The ablation procedure is considered complete when confirmation of entrance block in the pulmonary veins is confirmed and documented.
- Bidirectional block should be confirmed if linear lines are placed (Posterior Wall, Roof, Isthmus)

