Date: 2018.08.03 10:35:14 -07'00'
Adobe Acrobat version: 11.0.10

(Print)

(Sign)

Date

Franchise Head of Regulatory Affairs:

[name]

Digitally signed by [name]
DN: c=US, o=JNJ, ou=Subscribers, cn=[name],
0.9.2342.19200300.100.1.1=332810
Reason: I am approving this document.
Date: 2018.08.03 15:05:47 -07'00'
Adobe Acrobat version: 11.0.10

(Print)

(Sign)

Date

Revision History

Revision Number	Revision Date (DD/MM/YYYY)	Reasons for Revision
Version 1.0		Original Document

Table of Contents

1	Study Design	5
2	Treatment Assignment	5
3	Randomization and Blinding Procedures	5
4	Interval Windows	5
5	Primary and Secondary Endpoint(s) and Associated Hypotheses.....	5
	5.1 Primary Endpoint(s) and associated hypotheses	5
	5.2 Secondary Endpoints and associated hypotheses.....	5
6	Levels of Significance	7
7	Analysis Sets	7
8	Sample Size Justification.....	7
9	Data Monitoring Committee (DMC).....	8
10	Analyses to be Conducted	8
	10.1 General Conventions	8
	10.2 Disposition of Study Subjects	8
	10.3 Demographic and Baseline Characteristics.....	8
	10.4 Primary and Secondary Endpoint Analyses	9
	10.4.1 Acute Device Performance.....	9
	10.4.2 Safety.....	9
	10.4.3 Procedural Data	9
	10.4.4 Investigational Device Performance.....	9
	10.5 Plans for Interim Analysis	9
	10.5.1 Stopping Rules	10
	10.6 Handling of Missing Data	10
	Appendix: Tables, Listings and Graphs Shells	11

1 Study Design

The QDOT MICRO study is a prospective, multi-center, non-randomized clinical study to evaluate the workflow and acute performance of the THERMOCOOL SMARTTOUCH® SF-5D system in patients diagnosed with Paroxysmal Atrial Fibrillation (PAF).

The changes in this document from the protocol are the definitions of safety and effectiveness populations. The study was stopped due to safety reasons after 8 subjects were enrolled and treated under protocol version 1.0 and then the study catheter was re-designed. Therefore, the subjects who were enrolled and treated under protocol version 2.0 were using a different design of the study catheters.

2 Treatment Assignment

All subjects will receive ablation using the THERMOCOOL SMARTTOUCH® SF-5D catheter with temperature sensing capabilities and micro electrodes and CARTO 3 V 6.0 technology. However, the catheter was redesigned after the first 8 subjects were treated.

3 Randomization and Blinding Procedures

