The QDOT MICRO study is non-randomized and unblinded, all subjects will receive ablation via the THERMOCOOL SMARTTOUCH® SF-5D system.

4 Interval Windows

Refer to protocol Table 1 for summary of required schedule for subject treatments and evaluations.

5 Primary and Secondary Endpoint(s) and Associated Hypotheses

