5.1 Primary Endpoint(s) and associated hypotheses

Acute Device Performance

Acute Device Performance is defined as confirmation of entrance block in all targeted PVs after adenosine and/or isoproterenol challenge.

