10.4 Primary and Secondary Endpoint Analyses

10.4.1 Acute Device Performance

Acute success is defined as achieving confirmation of entrance block in all targeted PVs after adenosine and/ or isoproterenol challenge. The number and percentage of subjects who have reached acute success will be summarized. The analysis will be performed in the effectiveness populations.

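### SAP 10.6 limits all summaries to available data without exempting the primary endpoint, which conflicts with the denominator implied by SAP 10.4.1 and can only hold or raise the acute success percentage relative to that denominator

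*SAP*

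**What the plan says.** The endpoint is set out in SAP 5.1: "Acute Device Performance is defined as confirmation of entrance block in all targeted PVs after adenosine and/or isoproterenol challenge". SAP 10.4.1 repeats it and adds: "The number and percentage of subjects who have reached acute success will be summarized". It then names the analysis set: "The analysis will be performed in the effectiveness populations".

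SAP 7 defines Effectiveness Populations 1 and 2, one for each protocol version. A subject must be eligible, have had the device inserted, and have been ablated under guidance of the study module. A result after the challenge is not a condition of membership.

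SAP 10.6 contains two sentences. The first is "Missing questions will be queried for reasons and handled on an individual basis", which also stands in Protocol 12.3. The second is "Summary statistics will be reported based upon available data only", which Protocol 12.3 does not contain. Neither sentence mentions the primary endpoint.

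Protocol 9.2.3.1.8 sets the order of events: a "20-minute waiting period is REQUIRED from the last RF application at a PV before verification may be confirmed", with the drug challenge also given after that wait. Verification is mandatory for all pulmonary veins. Neither document says what follows in the analysis if it is absent.

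**The concern.** A subject can be ablated, and so belong to the effectiveness population, yet leave the laboratory without the post-challenge assessment that defines the endpoint. A procedure stopped during or before the waiting period is the plain example.

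For that subject two sections of the SAP point in different directions. The definition and analysis set in 10.4.1 imply a non-success who is counted in the denominator. A percentage is a summary statistic, so the available-data rule in 10.6 implies that the subject drops out.

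This is the only primary endpoint, and the study is descriptive, so the printed percentage is the result. Two analysts following different sections could print different figures from the same data. SAP 3 states that "The QDOT MICRO study is non-randomized and unblinded", so if the conflict is resolved at the analysis stage, it will be resolved by people who can see the outcomes.

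**Working it through.** **Inputs from the documents**

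- Planned total: about 10 subjects at each of about 5 sites, so 10 × 5 = 50 evaluable subjects (SAP 8). This reproduces the plan's figure. There is no power calculation or expected success rate to check.
- The total of 50 combines both protocol versions (SAP 8), and 8 subjects were treated under version 1.0 (SAP 1). If k of those 8 are evaluable, version 2.0 contributes 50 − k: 42 if all 8 are evaluable, 50 if none are.

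**Assumptions**

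- Evaluable subjects are taken to be the effectiveness-population members.
- The number without a result (m) and the number of observed failures are not in the documents. Small values are used for illustration.

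**Formulas.** Let n be the subjects in the population, m those without a post-challenge result, and x the confirmed successes.

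- Kept as not successful (implied by 10.4.1): x / n
- Removed (10.6 applied literally): x / (n − m)
- Difference: x/(n − m) − x/n = x·m / [n(n − m)]

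The difference is never negative. It is zero only if m = 0 or x = 0.

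**Results**

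| n | Observed failures | m | Removed | Kept as not successful |
|---|---|---|---|---|
| 42 | 0 | 1 | 41/41 = 100% | 41/42 = 97.6% |
| 50 | 0 | 1 | 49/49 = 100% | 49/50 = 98.0% |
| 42 | 0 | 2 | 40/40 = 100% | 40/42 = 95.2% |
| 50 | 0 | 2 | 48/48 = 100% | 48/50 = 96.0% |
| 42 | 2 | 1 | 39/41 = 95.1% | 39/42 = 92.9% |
| 8 (Population 1, if all qualify) | 0 | 1 | 7/7 = 100% | 7/8 = 87.5% |

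**The comparator matters.** The direction holds against keeping the subject as not successful. Suppose instead that the unassessed subject would have shown block. Take n = 50, 2 observed failures and m = 1, so x = 50 − 2 − 1 = 47. Removal gives 47/49 = 95.9%. Counting the subject as a success gives 48/50 = 96.0%. Keeping the subject as not successful gives 47/50 = 94.0%. Against the unknown true status, removal can therefore come out slightly low.

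**The case against.** The strongest reply is that 10.4.1 already answers the question. It names the population, and success requires confirmation to be achieved, so an unconfirmed subject is in the denominator and not in the numerator. This is right as far as it goes. A reader might infer that the plan has no denominator rule for its primary endpoint, and the documents do not support that. What remains is that the rule is implied, while 10.6 states a general rule that pulls the other way and exempts nothing.

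A second stronger reading is that 10.6 lets the sponsor drop subjects one by one. The text does not support this either. The sentence about individual handling concerns questions that are queried, and it comes from the protocol's data management chapter. It reads as a description of data queries. The point rests on the second sentence alone, which is a uniform rule. It may have been meant only to rule out imputation, but it does not say so.

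Third, a procedure stopped early, or block documented without the challenge, could be regarded as a known failure to meet the definition and not as missing data. That is a fair reading, and it reaches the same answer as the fix. But the outcome then depends on whether the field is recorded as not achieved or left blank, and the documents do not say which.

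Fourth, the table shells are separate (SAP Appendix) and may set the denominator. This limit stands.

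Finally, SAP 1 says "The changes in this document from the protocol are the definitions of safety and effectiveness populations", and the available-data sentence is not among those listed changes. Little weight belongs on this: adding such a sentence is ordinary elaboration and contradicts nothing in Protocol 12.3.

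**Conclusion.** The point holds and is minor. Two parts of the SAP give different denominators for an ablated subject without a post-challenge result, and the one stated as a general rule gives the more favourable percentage. One such subject is worth about 2.0 to 2.4 percentage points in Effectiveness Population 2 and 12.5 points in Effectiveness Population 1, if all other subjects succeed and all 8 version 1.0 subjects qualify for Population 1.

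These sizes rest on assumed counts. The case should be uncommon, because the protocol requires verification in every pulmonary vein. SAP 6 and 10.1 rule out formal inference, so no error rate or decision threshold is affected.

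A reader might also infer that the available-data figure overstates the catheter's true acute performance. The documents do not support that. The comparison is with the endpoint as defined, where unconfirmed means not successful, and says nothing about the block status of a subject who was never assessed.

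**What to change.** In SAP 10.4.1, as an explicit exception to 10.6, state two things. Every member of the effectiveness population stays in the denominator. A subject without documented entrance block in all targeted veins after the challenge counts as not successful, whatever the reason.

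For each effectiveness population, print the numerator, the denominator, the number of subjects without a post-challenge result, and the reasons. Check that the table shells use the same rule. The analysis populations stay as planned.

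The cost is one or two sentences and a check of the shells, using data already collected. The disadvantage is that the printed rate may be slightly lower than under the available-data rule.
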